- a. Screening/Baseline assessments may all be performed on the same calendar day and should be performed at the study site or as a home visit within 72 hours of first dose. Baseline assessments that are also performed at Screening do not need to be repeated if on the same calendar day. Study drug should be dispensed at the Screening/Baseline visit and only taken after the Day 1 virtual visit confirming the positive COVID-19 test has occurred. If the PCR test is negative or laboratory results exclude the patient, they will not take the first dose of study drug and be withdrawn from the study.
- b. Patients will be randomized to receive either 900, 1800, or 3600 mg of dalcetrapib treatment or placebo.
- c. The entry testing is performed locally based on testing methods available at the site, such as PCR or rapid antigen test.
- d. Patients must have at least two mild to moderate signs or symptoms of COVID-19, as described in the inclusion criteria, with onset within 5 days of first dose on Day 1. Symptoms will be assessed daily for the first 10 days, then at Day 14 and Day 28 and as clinically indicated.
- e. Dates of change in WHO scale status between visits will be recorded over the course of the 28-day study period.
- f. SARS-CoV-2 viral loads will be obtained by both saliva (Oragene) and mid-turbinate nasal swab self-collected under supervision of a healthcare professional at Screening/Baseline, Day 1, Day 3, Day 5, Day 7, Day 10, and Day 28.
- g. Two PK samples will be collected on Day 10, one at predose and one at postdose in a sampling window of 0-2, 2-4, 4-6, 6-10, or 10-24 hours postdose. Patients will be evenly randomized to one of the sampling windows on Day 10.
- h. Study drug is self-administered as once daily oral tablets on Days 1 to 10.
- i. In case of screen failure only.

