## 2 STUDY DESCRIPTION

### 2.1 Study Design

This is a randomized, double-blind, multicenter Phase 2a proof-of-concept study in outpatients with confirmed, mild to moderate, symptomatic COVID-19. Electronic informed consent must be obtained from all patients or their legally authorized representative during screening before any study-related procedures are performed. The Screening/Baseline assessments may be performed at the study site or as a home visit.

A total of 208 patients will be randomized to receive 900, 1800, or 3600 mg of dalcetrapib or placebo once daily (52 patients to each of 900 mg, 1800 mg, 3600 mg and placebo) for 10 days. Patients will be randomized and receive first dose of study drug within 72 hours of receiving a positive PCR or Point-of-care test for SARS-CoV-2. Patients need to have at least two of the 14 common COVID-19-related symptoms described in the inclusion criteria rated as mild or moderate, as evaluated by ePRO assessment or eCRF. Symptoms will be assessed at each study visit daily for the first 10 days, then at Day 14 and Day 28, and as clinically indicated. Symptoms will be evaluated as absent, mild, moderate, or severe depending on their impact on activities of daily living. SARS-CoV-2 viral loads will be obtained by both saliva (Oragene) collection and mid-turbinate nasal swab self-collection under supervision of a healthcare professional (virtual or home visit) at Screening/Baseline, Day 1, Day 3, Day 5, Day 7, Day 10, and Day 28. Patients who require hospitalization after initiation of study treatment will be followed for safety assessment through Day 28.

The study will be overseen by an independent Data Monitoring Committee (DMC). The DMC will review the safety data throughout the study. The DMC and Sponsor will review efficacy data at the interim analysis and at the end of the study. A DMC Charter, which includes detailed processes, will be prepared. One interim analysis will be conducted once 120 patients have a follow-up time of 28 days.

All patients will be closely monitored for adverse events (AEs) from informed consent for at least 18 days after the final dose of study treatment (until Day 28±2). Patients who withdraw early from the

study treatment will have follow-up phone calls to collect safety data until End of Study on Day 28±2. On days of laboratory assessments and PK sample collection, outpatient subjects may have a home visit.

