### **4 EFFICACY ENDPOINTS**

#### **4.1 Primary Efficacy Endpoint**

The primary efficacy endpoint is:

- Time to sustained clinical resolution of symptoms (excluding cough, sense of smell and taste)

Sustained clinical resolution is defined as occurring when no key COVID-19 related symptom (excluding cough, sense of smell and taste) has a score higher than 1 over a 72-hour period (as documented using an electronic patient-reported outcome [ePRO] instrument or in the eCRF). The time to resolution will be taken as the time from randomization until the first day of the last 72-hour period where the patient meets the definition of resolution within 28 days. Patients who do not meet the definition of resolution 28 days after randomization will be considered not resolved.

The classification of sustained clinical resolution of symptoms (excluding cough, sense of smell and taste) follows similar steps as the algorithm presented in Appendix 1.

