## 9 APPENDICES

### APPENDIX 1

Algorithm used to classify sustained clinical resolution:

For each subject, all ePRO records will be sorted by the date/time. For each assessment, we characterize the record as clinically resolved (i.e., score of 0 for taste and smell and all other symptoms, a score of 0 or 1) or not.

From Day1 to Day10 (or last ePRO assessment before Day14)

- a) If resolved at Day 10 (or last ePRO assessment), identify first date when resolution occurred with no relapse. This is the tentative date of resolution to be confirmed at Day 14 and Day 28.
- b) If not resolved at Day 10 (or last ePRO assessment), re-assess at Day 14.

At Day14:

- c) If resolved for the first time at Day 14 (i.e. was not resolved at Day 10 or before), use date of Day 14 as the tentative date of resolution to be confirmed at Day 28.
- d) If still resolved at Day 14 (i.e. was already resolved at Day10 or before), use date of resolution identified in step a). This is the tentative date of resolution to be confirmed at Day 28.
- e) If not resolved at Day 14, re-assess at Day28.

At Day28:

- f) If resolved for the first time at Day 28 (i.e., was not resolved at Day 14), subject will be classified as resolved within 28 days and date of resolution will be the date of Day 28.
- g) If still resolved at Day 28 (i.e. was already resolved at Day 14), subject will be classified as resolved within 28 days and date of resolution will be the date of resolution identified in step c) or d).
- h) If not resolved at Day 28, subject will be classified as not resolved within 28 days and the date of censoring will be the date of Day 28.

It should also be noted that subjects who do not have an assessment at Day 28 will be classified as non-resolved REGARDLESS if symptoms were resolved up to their last assessment. Date of censoring will be the date of study discontinuation.

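### SAP Appendix 1 reads no symptom record between the Day 14 and Day 28 records, so a relapse documented there leaves an early resolution date standing

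*SAP*

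**What the plan says.** Protocol Appendix 4, footnote d, sets the symptom schedule: "Symptoms will be assessed daily for the first 10 days, then at Day 14 and Day 28 and as clinically indicated". SAP 2.1 repeats it, so both documents provide for unscheduled symptom scores.

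SAP 4.1 defines the time to sustained resolution as running from randomization to "the first day of the last 72-hour period where the patient meets the definition of resolution within 28 days". It also says that the primary endpoint is classified by steps similar to those in Appendix 1.

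Appendix 1 begins broadly: "For each subject, all ePRO records will be sorted by the date/time", and each record is classed as resolved or not. The decision steps are narrower:

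- Step a, whose period is Day 1 to Day 10 or the last ePRO record before Day 14: "If resolved at Day 10 (or last ePRO assessment), identify first date when resolution occurred with no relapse".
- Steps c to e use the Day 14 record. Step d keeps the step a date if the patient is still resolved then.
- Steps f to h use the Day 28 record. Step g reads: "If still resolved at Day 28 (i.e. was already resolved at Day 14), subject will be classified as resolved within 28 days". The date stays as set in step c or d.

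**The concern.** The requirement of no relapse is written into step a only. After that, the algorithm looks at two records, and step g explains what it means by still being resolved purely by reference to Day 14. A score taken between those visits because the patient felt worse is collected and sorted, and then consulted by no step.

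The endpoint is meant to capture sustained resolution, and dosing ends on Day 10. Where a relapse has been documented after Day 14, the plan has direct evidence that the earlier resolution was not sustained, yet it still credits the earlier date. The derivation and the definition in SAP 4.1 then give different answers for the same patient, in the primary endpoint and in the three other resolution endpoints of SAP 4.2.

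**Working it through.** **The design figure.** The only planned figure tied to this endpoint is 127 events for 80% power at a hazard ratio of 1.4 (Protocol 8.1). It reproduces as a group-sequential design with 2:1 allocation and one-sided alpha 0.2:

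- Information fraction at the interim: 73/127 = 0.575.
- Alpha spent there with rho = 2: 0.2 × 0.575² = 0.066, so z = 1.506.
- Efficacy boundary: exp(1.506/√(73 × 2/9)) = 1.453 (stated 1.45).
- Final nominal alpha 0.1862 (stated 0.186); power 80.0%.

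This point does not disturb that calculation, because the affected patients are still counted as resolved by Day 28.

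**The algorithm on test patients.** Take a patient not resolved on Days 1–4 and resolved on Days 5–10, Day 14 and Day 28, then change or add a record. The comparison uses every record and dates resolution from the first resolved record after the last unresolved one.

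| Change to the records | Appendix 1 | All records | Days too early |
|---|---|---|---|
| None | Day 5 | Day 5 | 0 |
| Unresolved at scheduled Day 14 | Day 28 | Day 28 | 0 |
| Unresolved on Day 15, 18, 20 or 25 | Day 5 | Day 28 | 28 − 5 = 23 |
| Unresolved Day 20, resolved Day 23 | Day 5 | Day 23 | 23 − 5 = 18 |
| Unresolved Day 20, resolved Day 21 | Day 5 | Day 21 | 21 − 5 = 16 |
| Unresolved on Day 11 | Day 5 or Day 14 | Day 14 | 9 or 0 |

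The Day 11 row depends on step a. If step a stops at Day 10, the record is not read; if it runs to the last record before Day 14, it is. A first record on Day 12 or 13 is covered where the Appendix 2 windows are applied, since a difference of 11 to 15 days from first dose (Days 12–16) counts as Day 14.

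An unresolved score at Day 14 therefore moves the date to Day 28, while an unresolved score on Day 18 moves nothing.

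**Effect on the comparison.** The documents give no relapse rate and no expected number of unscheduled assessments, so the following is an assumed range. Setting: 104 active against 52 placebo, exponential resolution times, placebo median 9 days, true hazard ratio 1.4, 1,500 simulated trials per scenario, every relapser moved to Day 28 (the largest shift). Two separate simulations were run; both results are given where they differ.

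| Recorded relapse among early resolvers, active/placebo | Mean HR, Appendix 1 | Mean HR, relapse counted |
|---|---|---|
| 5% / 5% | 1.43–1.44 | 1.42 |
| 10% / 5% | 1.43 | 1.31–1.32 |
| 15% / 5% | 1.43 | 1.22–1.23 |
| 5% / 10% | 1.43–1.44 | 1.50–1.52 |

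The chance of a favourable result at two-sided 0.20 is 70% against 52–54% in the second row, and 70% against 39–40% in the third.

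In patients: by Day 14 the model resolves 104 × (1 − 2^(−14 × 1.4/9)) ≈ 81 active and 52 × (1 − 2^(−14/9)) ≈ 34 placebo patients. The second and third rows thus need about 8 and 12 recorded relapses on active drug, against about 2 on placebo.

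**The case against.** The strongest reply is that a derivation based on scheduled visits measures every patient alike. Unscheduled scores exist only for patients who had extra contact; an identical relapse without contact would keep the early date. The next resolved record after a relapse may also be Day 28, so a relapse that ended on Day 21 would be dated about a week late. These points stand. They justify keeping the scheduled-visit version as a sensitivity analysis, but they do not reconcile Appendix 1 with SAP 4.1, and the plan does not present its rule as a deliberate restriction to scheduled visits.

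A second reply is that a programmer, told to sort all records and guided by SAP 4.1, would treat a documented relapse as breaking resolution. That is possible, but step g's own explanation points the other way, and two programmers could derive different primary dates.

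Third, part of the problem is already handled. SAP 6.2.2.2 imputes maximum severity at the assessment day after death or another antiviral therapy. That does not reach a relapse managed without another antiviral.

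Stronger readings are tempting and are not supported:

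- A reader might infer that all relapse after Day 10 is missed. Step a can extend to the last record before Day 14, and unresolved Day 14 or Day 28 records do move or cancel the date. For the same reason, unscheduled scores are not the only evidence of relapse after dosing stops.
- A reader might infer that Appendix 2, which has no window for Days 17–25, formally bars such records. Neither Appendix 1 nor SAP 6.4.1 invokes Appendix 2. The gap follows from Appendix 1 alone.
- A reader might infer that the treatment effect is inflated. The direction depends on which arm has more recorded relapse, and the documents do not say.

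**Conclusion.** As written, steps d and g leave an early resolution date in place despite a relapse recorded between the Day 14 and Day 28 records, contrary to SAP 4.1. On the narrow reading of step a, a Day 11 relapse is lost as well. In the worked case the date is 16 to 23 days too early, depending on the next resolved record. The count of resolved patients does not change; event times, medians and the log-rank ordering do.

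The effect on the hazard ratio cannot be computed from the documents. It is negligible if recorded relapse is rare and equal across arms. The large shifts in the simulations rest on assumed relapse two or three times as common in one arm and on moving every relapser to Day 28; nothing in the documents supports or excludes that.

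The sensitivity analyses in SAP 6.4.4 do not help: one repeats the analysis in the per-protocol population, the other carries the last observation forward to a missing Day 28, and both still use the Appendix 1 steps. The correction is worth making because the primary derivation departs from its own definition and the remedy is cheap.

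**What to change.** Add to steps d and g of Appendix 1 that any unresolved symptom record, scheduled or unscheduled, dated after the tentative date and up to the Day 28 record cancels that date, and that the date of resolution becomes the first resolved record after the last unresolved one. This also settles the Day 11 ambiguity.

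Apply the rule to all four resolution endpoints: sustained and complete, each with and without cough, smell and taste. Report the number of patients re-dated, by arm, and keep the scheduled-visits-only derivation as a sensitivity analysis.

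The cost is one sentence and a small programming change, with no new data. The downside is that dates can move only for patients with extra contact, and the new date may be somewhat late when the next record is Day 28. In a double-blind trial, extra contact is not expected to differ by arm except through real symptoms, and the sensitivity analysis shows how much the choice matters.

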## Appendix 4 – Schedule of Assessments

**Table 5: Schedule of Assessments**

Study Period	Screening/ Baseline	Treatment Period					Follow-up Visit 1	Follow-up/EOS Visit 2
		1	3	5	7	EOT 10		
Study Day	-2 to -1 a						14 ± 2 days	28 ± 2 days
Informed consent	X							
Randomization b	X							
Inclusion/exclusion criteria	X	X						
SARS-CoV-2 test c	X							
Demographics	X							
Medical history	X							
Pregnancy test (urine)	X							X
COVID-19 symptoms ePRO assessment d	X	X	X	X	X	X	X	X
Efficacy								
Clinical improvement score (WHO COVID-19 Clinical Improvement Ordinal Scale) e	X	X	X	X		X		X
Confirm setting (outpatient, in hospital)	X		X		X		X	X
Saliva (Oragene) f	X	X	X	X	X	X		X
Mid-turbinate nasal swab f	X	X	X	X	X	X		X
Safety								
Adverse events	X	X	X	X	X	X	X	X
Blood sampling for laboratory assessments	X					X		X
Pulse oximetry	X	X	X	X	X	X	X	X
Prior and concomitant medications	X	X	X	X	X	X	X	X
Pharmacokinetics								
PK sampling g						X		
Other								
Patient training on use of ePRO and pulse oximeter and swab self-collection	X							
Dispense study drug	X							
Study drug administration h		X	X	X	X	X		
Return unused treatment		X i				X		

COVID-19 = Coronavirus disease of 2019; EOS = end of study; EOT = end of treatment; PCR = polymerase chain reaction; PK=pharmacokinetic; ePRO = electronic patient-reported outcome; SARS-CoV-2= Severe Acute Respiratory Syndrome CoronaVirus 2; WHO = World Health Organization

Note that any visits other than Screening/Baseline may be conducted via telephone or digital media. Missed samples/assessments when phone visits occur will not be counted as protocol deviations. Safety laboratory samples for hematology and chemistry, and study drug accountability, are obtained via a site visit or home visit by a healthcare professional.

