### 6 STATISTICAL METHODOLOGY

#### 6.1 Determination of Sample Size

As per protocol, it was anticipated that 208 patients will be randomized into the study in a 1:1:1:1 ratio to 900, 1800, or 3600 mg dalcetrapib or placebo. The original sample size was calculated for the sustained resolution endpoint and was described in the protocol as follows: The purpose of the proof-of-concept study is to identify whether there is sufficient promise of efficacy to justify conducting a Phase 3 study in a larger sample size and to determine efficacious dose to be used in Phase 3. While the entirety of data will be considered at the end of study, the sample size has been chosen to ensure that a positive trend will be present with alpha of 0.2 when considering the two highest doses combined compared to placebo. One-hundred twenty-seven (127) resolution events provides 80% power to demonstrate a positive trend if the average hazard ratio (HR) of the two dalcetrapib groups is 1.4 relative to placebo. Allowing for 20% of patients not resolving, 156 patients (52 per treatment arm) will be enrolled across the two highest dose levels and placebo arms, and an additional 52 will be randomized to 900 mg for a total sample size of 208 patients.

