#### 6.2 Statistical Considerations

Continuous variables will be summarized by the standard descriptive statistics: number of patients (n), mean, standard deviation, median, Q1, Q3, minimum, and maximum, along with confidence interval (CI) for outcome measures when appropriate. Frequency of patient or events and percentages will be summarized for categorical variables, again with CI when appropriate. Time to event variables will be summarized using Kaplan-Meier methods.

All statistical tests will be conducted at a two-sided 0.20 significance level.

Statistical analyses will be performed using SAS Version 9.4 or higher.

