#### 6.4.4 Sensitivity Analysis

As a sensitivity analysis, the primary analysis described in section 6.4.1 will be repeated on the PP population.

As an additional sensitivity analysis, the primary endpoint will be derived using the algorithm of Appendix 1, but prior to applying the algorithm, the last observation carried forward will be used in alive patients with no assessment at Day 28. In other words, in alive patients, the missing assessment at Day 28 will be imputed as the last available assessment.

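### SAP Appendix 1 counts recovered patients as non-resolved when only the Day 28 score is missing, so events are lost and the treatment effect depends on Day 28 attendance

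*SAP*

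**What the plan says.** SAP 4.1 requires a 72-hour resolved period and dates the event to the "first day of the last 72-hour period where the patient meets the definition of resolution within 28 days". Anyone who falls short of that 28 days after randomization counts as not resolved. The section does not name a Day 28 record as a condition. It then says that the classification follows steps similar to those in Appendix 1.

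Appendix 1 sets a tentative resolution date from the scores up to Day 10 or at Day 14, to be confirmed at Day 28. Without a Day 28 assessment the patient "will be classified as non-resolved REGARDLESS if symptoms were resolved up to their last assessment", and the censoring date is study discontinuation.

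SAP 6.4.1 censors non-resolvers at the last time point where they were not resolved. For the medians it assigns censored patients 29 days.

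SAP 6.4.4 plans a sensitivity analysis in which, "in alive patients, the missing assessment at Day 28 will be imputed as the last available assessment".

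SAP 4.2 applies the Appendix 1 algorithm, or a definition tied to the primary endpoint, to the other three symptom-resolution endpoints.

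**The concern.** Suppose a patient is unresolved on Days 1-4, resolved on every score from Day 5 to Day 10 and at Day 14, has no Day 28 score, and leaves the study on Day 20. The SAP treats this one record in five ways:

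| Source | Result |
|---|---|
| SAP 4.1, dated from the start of the unbroken run as in Appendix 1 step a) | event at Day 5 |
| Appendix 1, last paragraph | no event, censored at Day 20 |
| SAP 6.4.1, censoring | no event, censored at Day 4 |
| SAP 6.4.1, medians | 29 days |
| SAP 6.4.4, sensitivity analysis | event at Day 5 |

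Under Appendix 1 a recovered patient stays in the risk set as still unresolved. The rule removes only patients who had recovered, because a non-resolver's status does not change. At stake are the primary log-rank test, the percent resolved (Table 2.1.1) and the curve (Figure 2). All of them come to depend on who attends at Day 28 as well as on who recovers.

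**Working it through.** **Inputs.** From SAP 6.1: hazard ratio 1.4, 127 events, 80% power, alpha 0.2, 20% not resolving, 52 per arm (so 52 v 104). From SAP 6.2: two-sided 0.20. Assumed: constant hazards, random missingness within arm, and the missing-Day-28 rates shown.

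**The plan's own figure.** The SAP states that "One-hundred twenty-seven (127) resolution events provides 80% power to demonstrate a positive trend"; the effect it assumes is the hazard ratio of 1.4 listed above. With 2:1 allocation, the expected z is ln(HR) × √(events × 2/9).
- For 127 events: 0.3365 × √28.22 = 1.787.
- One-sided 0.20: Φ(1.787 − 0.842) = 83% for a fixed design. Adding the protocol's interim look at 73 events, with spending 0.2 × (73/127)² = 0.066 and non-binding futility at HR 1, gives 80.0%. The interim bound is HR 1.453 (stated 1.45) and the final alpha 0.186 (as stated). The figure reproduces.
- Two-sided 0.20, the level in SAP 6.2: Φ(1.787 − 1.282) = 69%. Power below is on this scale, so the starting point is 66-69%, not 80%.

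**Percent resolved.** Solve (x + 2x^1.4)/3 = 0.20 for placebo non-resolution at Day 28: x = 0.274. Placebo resolves 72.6% and pooled drug 83.7%; (72.6 + 2 × 83.7)/3 = 80.0. By Day 14, 1 − x^0.5 = 47.7% and 1 − x^0.7 = 59.6% have resolved. With 10% missing in each arm, Appendix 1 reports 0.9 × 72.6 = 65.3% and 0.9 × 83.7 = 75.3%. The difference falls from 11.1 to 10.0 points.

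**Hazard ratio, equal missingness, true value 1.40** (large-sample Cox fits, continuous time; expected events among 156, 124.9 with none missing):

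| Missing | Appendix 1, leaving Days 11-28 | Appendix 1, censored Day 28 | SAP 6.4.1 date | Events, present rule | Observed events kept |
|---|---|---|---|---|---|
| 5% | 1.38 | 1.37 | 1.40 | 118.6 | 1.40, 123.8 events |
| 10% | 1.36 | 1.34 | 1.40 | 112.3 | 1.40, 122.7 events |
| 20% | 1.33 | 1.30 | 1.40 | 99.9 | 1.40, 120.6 events |

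**Power at two-sided 0.20, 10% missing in each arm** (simulated log-rank, 52 v 104, scores on Days 1-10, 14 and 28):
- Nothing missing: 66-67%.
- Appendix 1: about 54% if censored at Day 28, 61% if departures spread over Days 11-28, 62% if at Day 14.
- SAP 6.4.1 date: about 65%.
- Observed events kept: about 65%.

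The formula agrees closely. Censored at Day 28: 0.290 × √(112.4 × 2/9) = 1.45, and Φ(1.45 − 1.28) = 57%. SAP 6.4.1 date: 0.3365 × √(112.4 × 2/9) = 1.68, and Φ(1.68 − 1.28) = 66%. The 54% end is therefore good to a few points.

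**Unequal missingness:**

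| Missing, placebo v drug | True HR 1.40, Appendix 1 (leaving Days 11-28) | True HR 1.40, SAP 6.4.1 date | Inactive drug |
|---|---|---|---|
| 10% v 20% | 1.16 | 1.27 | 0.91 |
| 20% v 10% | 1.57 | 1.55 | 1.10 |
| 8% v 12% | - | - | about 0.95-0.97 |
| 12% v 8% | - | - | about 1.02-1.06 |

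The inactive-drug figures for 10% and 20% use Appendix 1's date on the visit grid. Other choices of censoring date and of handling tied visit days move the ends of the last two ranges by one to three hundredths. Neither censoring date protects against unequal attendance. Keeping observed events leaves the hazard ratio at 1.40 in the first two rows.

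**The case against.** The best defence is that the endpoint is sustained resolution, and that which 72-hour period is last cannot be known without later data. Appendix 1 calls earlier dates tentative, and SAP 6.2.2.2 censors patients who lack a required assessment. On that reading the patient is unconfirmed, not an observed event. This has some force, and a reader might infer a flat contradiction with SAP 4.1 that the wording does not quite support. It does not rescue the rule. Step f) accepts a single Day 28 record as an event with no 72-hour evidence, while a run from Day 5 to Day 14 is discarded. Calling the patient non-resolved and censoring after the recorded recovery also goes beyond treating the status as unknown.

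A reader might also infer that the rule simply shrinks the drug effect, or is safely conservative. Neither is supported. Attenuation needs similar missingness by arm (or more on drug) together with Appendix 1's date. With the SAP 6.4.1 date and equal missingness there is no bias in the hazard ratio, and with more missing on placebo the effect is inflated. Nothing in the documents says which arm will lose more Day 28 scores.

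The SAP already plans the carried-forward version (Table 2.1.3), and its introduction puts less weight on symptom endpoints. Both points limit the harm, but they leave the primary result on the discarding rule.

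Exposure is uncertain. The protocol's schedule notes that "Missed samples/assessments when phone visits occur will not be counted as protocol deviations", but symptom scores can be entered electronically or by telephone, and Day 28 has a two-day window either side. At 5% missing the effect is small.

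**Conclusion.** The concern holds in a limited form. For patients with no Day 28 score, the primary derivation discards recorded recoveries, understates the percent resolved in every arm, and conflicts with SAP 6.4.1 on the censoring date. The consequence for the treatment comparison is a loss of events plus a bias whose direction depends on missingness by arm and on the date used. At 10% missing in each arm, about 12 of 125 expected events are lost (124.9 − 112.3 = 12.6), against about 2 if observed events are kept (124.9 − 122.7 = 2.2). These sizes rest on constant hazards, the plan's 1.4 and 80%, random missingness within arm, and assumed missing rates. The case for changing the rule does not depend on a particular rate.

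**What to change.** Reconcile SAP 4.1, SAP 6.4.1 and Appendix 1 before unblinding, with one status rule and one censoring date. Replace the last paragraph of Appendix 1, for a living patient with no Day 28 score and no rescue antiviral, with:
- (a) If resolved at the last available assessment, count the event at the tentative date from step a), c) or d). Use the evidence standard that Appendix 1 already applies to those steps. Include step a)'s case where the last ePRO record falls before Day 14, and step c)'s single Day 14 record.
- (b) Otherwise, censor at the last symptom assessment.

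Deaths and rescue antiviral use stay as in SAP 6.2.2.2. Use this derivation in Table 2.1.1, Figure 2 and the other resolution endpoints, and keep the present rule as the sensitivity analysis. Report missing Day 28 scores by arm alongside.

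The cost is SAP wording and modest programming. No new data are needed, and the derivation is close to the one planned for Table 2.1.3. It is not identical, because carrying forward keeps unresolved patients at risk to Day 28 while (b) censors them earlier. The downside is that a few patients who relapse unseen before Day 28 will count as resolved. The retained strict rule shows how much that matters.
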